#### **5.1.2.4 Per-Protocol Population**

The Per Protocol analysis population (PP) will include all patients in the Efficacy Population who were dosed according to protocol with no major protocol deviations with respect to eligibility criteria and efficacy assessments, and will be finalized prior to database lock.

The full set of efficacy analyses will be conducted for the EP and COVID-EP, whereas analyses for the PP analysis population will be restricted to the change in PANSS Total Score at weeks 2, 4, 8, 10, and 12.

Individual assignment to each analysis population will be provided in a listing.

#### **5.1.2.5 Subjects Enrolled More Than Once**

In the event subjects are found to have enrolled (been randomized and treated) more than once within the study, the first enrollment will be designated as the

primary enrollment. Only the primary enrollment will be included in efficacy analyses. Safety data from additional enrollments will generally be included in analyses, depending on analysis type and treatments received.

#### **5.1.3 Statistical Analyses – General Considerations**

For the Treatment Period, data will be summarized by treatment group (CTP-692 1 g QD, CTP-692 2 g QD, CTP-692 4 g QD, or placebo). All data for analysis will be listed by patient.

The same number of decimal places as in the raw data will be presented when reporting minimum and maximum, 1 more decimal place than in the raw data will be presented when reporting mean and standard deviation.

Continuous variables will be summarized by treatment using descriptive statistics (n, mean, median, standard deviation, minimum, and maximum). For categorical variables, frequencies and percentages will be presented by treatment. Baseline is defined as the last observation prior to initiation of Study Medication.

Listings for CSR Appendix 16.2 will include all the patient data points being collected or derived for analyses. Data listings will be provided for all patients up to the point of study completion or withdrawal.

All statistical tests will be 2-sided with a significance value of 0.05. Patients will be summarized by randomized treatment group, except for the Safety Population, which will be summarized by actual treatment received. There will be no adjustments for multiple comparisons.

#### **5.1.4 Procedures for Handling Missing Data**

In general, missing data will not be imputed, as the Mixed Model Repeated Measures (primary analysis approach) is considered valid under a Missing at Random (MAR) missingness mechanism.

As a sensitivity analysis for the primary endpoint, the last observation carried forward (LOCF) method will be used to impute missing values for patients who withdraw from the study prior to the completion of the 12-week Treatment Period.

A listing will be provided indicating patients and visits with missing data or remote visits due to COVID-19, as well as early terminations due to COVID-19.

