Patients will receive their first dose of Study Medication in the clinic on Day 1. The dose of CTP-692 or Placebo should be administered with food. Patients will be instructed to take Study Medication once daily at home with food in the morning for the next 12 weeks. Patients will return to the clinic at Weeks 2, 4, 6, 8, 10, and 12 for safety and efficacy assessments and to pick up Study Medication as shown in [Table 6](#). Due to the COVID-19 pandemic and the possibility for site closures and/or travel restrictions, clinical laboratory blood draws may be performed by a Home Health Care service provider or by a local laboratory; other safety and efficacy assessments may be performed remotely via phone/audio or video conferencing platforms (with the exception of Facebook). Study personnel should strive to perform assessments within the visit window as shown in [Table 6](#) with the understanding that not all assessments may be able to

be performed. Missed assessments will be recorded in the eCRF with notation that the missed assessment was due to the COVID-19 pandemic.

Phone contact will be made with the patient on Weeks 1, 3, 5, 7, 9 and 11. Patients may be requested to make Unscheduled Visits to the clinic if the Investigator (or designee) thinks necessary.

The primary outcome measure will be the change in PANSS total score at Week 12 from Baseline. Patients will be required to return to the clinic approximately 1 week after the last dose of Study Medication for safety assessments including physical examination, adverse-events and concomitant medications as shown in [Table 6](#). Due to the COVID-19 pandemic the Safety Follow-up visit may be conducted remotely via phone/audio or video conferencing platforms (with the exception of Facebook) per Investigator discretion. If any of the safety parameters including clinical laboratory parameters at the end of the Treatment Period are reported to be abnormal, unscheduled assessments may be performed at the Safety Follow-Up Visit and additional follow-up may be required as the Investigators deem necessary. Patients who experience intolerable symptoms during the Treatment Period may discontinue the study at the discretion of the Investigator.

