13.4.2. Efficacy

All statistical tests will be 2-sided with a significance value of 0.05. Patients will be summarized by randomized treatment group. There will be no adjustments for multiple comparisons to placebo.

A mixed effects repeated measures model will be used to assess treatment group differences for change from baseline. The model will include treatment group, analysis visit, treatment-by-visit interaction, the baseline value as a covariate, and patient as a random effect. The comparison of each CTP-692 dose group versus placebo will be assessed by forming the least squares means estimate of each the CTP-692 dose group and comparing it to the placebo group at each postbaseline analysis visit. An unstructured covariance structure will be used to model the within-patient errors.

As a sensitivity analysis, the last observation carried forward (LOCF) method will be used to impute missing values for patients who withdraw from the study prior to the completion of the 12-week Treatment Period.

Additional details will be summarized in the Statistical Analysis Plan.

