## **5.1 Statistical Methodology**

### **5.1.1 Sample Size Determination**

Approximately 75 patients will be randomized to each treatment arm to achieve a sample size of approximately 60 patients per arm who complete the study. A sample size of 60 per arm provides at least 80% power for the change at Week 12 from Baseline in PANSS total score, assuming a treatment difference from placebo of 5.2 and standard deviation of 10, on a two-sided t-test at 0.05 significance level.

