#### **5.1.5 Study Day and Visit Window Definitions**

The baseline assessment for all efficacy endpoints is defined as last assessment prior to the first dose of Study Medication on Day 1. Data obtained during unscheduled and at the Week 12/Early Termination early visits will be allocated to the scheduled time point corresponding to the visit window in which they fall in as specified in Table 2. For patients completing the study, data will be analyzed based on the nominal visits and nominal time points. If the data from the nominal visit or time point are missing or the patient did not complete the study, data from

unscheduled visits or the Week 12/Early Termination visit within the time interval for the same nominal visit or time point will be used. If multiple visits among unscheduled or Early Termination assessments fall in the same visit window or time point, the non-missing assessment closest to target time point will be selected for analysis. If multiple values are the same number of days away from the target study day, then the latter value will be used. In the unlikely event an unscheduled or Early Termination visit, associated with a particular visit window, falls either prior to the actual previous nominal visit date or after the subsequent nominal visit date, it will not be used. This is done simply to ensure the data assigned to particular analysis time points will not be out of sequence.

The first date on which patient received the Study Medication will be used as the Study Day 1. Study days for other visits will be calculated as follows:

- Before Study Day 1 visit: Study Day = date of assessment – date of Study Day 1
- On or after Study Day 1 visit: Study Day = date of assessment – date of Study Day 1 + 1

Last study date is the last visit date of any scheduled, unscheduled, or Early Termination visits. Last Study Day is calculated as:

- Last Study Day = last study date – date of Study Day 1 + 1

The target study days of Study Center Visits are summarized below.

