**Table 2 – Guidelines for Assigning Unscheduled and Early Termination Visits for Efficacy Assessments**

Week/Visit	Time Interval (Day)	Target Time Point (Day)
-5/Screening	Use nominal	-35*
-3/Qualification	Use nominal	-24 to -21*
1 (Baseline/Day 1)	Last assessment prior to dosing	1
2	8 to 21	14
4	22 to 35	28
6	36 to 49	42

8	50 to 63	56
10	64 to 77	70
12	78 to 1 day prior to Safety Follow-up	84
13/Safety Follow-up	Use nominal	91

\*5-week Screening/Qualification Period may be extended up to 2 weeks if repeat laboratory test results for confirmation of eligibility are pending.

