## 5.4 Efficacy Analyses

### 5.4.1 Primary Analysis

The primary efficacy endpoint will be the change in PANSS total score at Week 12 from Baseline. A mixed model for repeated measures (MMRM) will be used to

assess treatment group differences for change from baseline. Fixed effects will include treatment group, analysis visit, treatment-by-visit interaction, and a baseline-by-visit interaction. Visit will be fit as a repeated effect using the repeated statement in SAS. The baseline score will be included as a continuous covariate. An unstructured covariance structure and Kenward-Roger degrees of freedom will be used. In the event an unstructured covariance structure fails to converge, a Toeplitz structure will be used.

Least squares means will be presented for treatment\*visit, with the significance level of the treatment-by-visit interaction presented in summary tables. Pair-wise comparisons of differences in LS means, two-sided 95% confidence intervals (CIs) on differences, and p-values will be provided for each active treatment versus placebo for each visit.

A listing for PANSS individual questions as well as subscale totals will be provided.

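### LOCF is the only missing-data sensitivity analysis behind a MAR-based MMRM, so the plan cannot show how far MAR could fail before a Week 12 PANSS result is overturned

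*SAP*

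**What the plan says.** SAP 5.1.4 leaves missing values unimputed in general because the MMRM "is considered valid under a Missing at Random (MAR) missingness mechanism". For the primary endpoint it adds one sensitivity analysis: "the last observation carried forward (LOCF) method will be used to impute missing values for patients who withdraw from the study" before the 12-week Treatment Period is complete. Protocol 13.4.2 names the same single method: "As a sensitivity analysis, the last observation carried forward (LOCF) method will be used to impute missing values".

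SAP 5.4.1 specifies the model: "Fixed effects will include treatment group, analysis visit, treatment-by-visit interaction, and a baseline-by-visit interaction", with an unstructured covariance. Its only fallback is a Toeplitz structure if that does not converge. The COVID-related Efficacy Population and the Per-Protocol Population (SAP 5.1.2.3 and 5.1.2.4) are further analysis sets. The COVID-19 missing-data item in SAP 5.1.4 is a listing.

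Four other provisions bear on how much Week 12 data will be missing:

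- SAP 5.1.1 randomises about 75 per arm "to achieve a sample size of approximately 60 patients per arm who complete the study".
- Protocol 9.3.1 asks for all Week 12 assessments at an Early Termination visit.
- SAP 5.1.5 says that, where a nominal value is missing or the patient did not complete, data from "unscheduled visits or the Week 12/Early Termination visit within the time interval for the same nominal visit or time point will be used". Table 2 gives the Week 12 interval as Day "78 to 1 day prior to Safety Follow-up".
- Protocol 7.1 recognises that the pandemic may prevent some assessments: "Missed assessments will be recorded in the eCRF with notation that the missed assessment was due to the COVID-19 pandemic".

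**The concern.** A sensitivity analysis for an MMRM should probe the assumption the MMRM rests on. LOCF does depart from MAR, since it assumes no change after the last observed score, but it does so in one fixed way. It has no parameter to increase, it treats carried-forward values as if observed, and its bias need not be conservative. If LOCF agrees with the MMRM, the reader does not learn how far MAR could fail. If it disagrees, the reader does not learn whether a plausible departure is enough to overturn the result.

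As worded, LOCF also covers only patients who withdraw. A Week 12 PANSS missed by a patient who stays in the study is handled under MAR with no alternative assumption examined. The COVID-related and Per-Protocol sets change who is analysed and keep the same model.

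Dropout unrelated to unseen outcome cannot be taken for granted. The withdrawal criteria in Protocol 9.3 include intolerable adverse events, confirmed renal and hepatic findings, suicidality and noncompliance, some of which could differ by arm or relate to later symptoms. At stake is whether a dose that separates at Week 12 can be called robust to missing data.

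**Working it through.** **Inputs from the documents.** Difference 5.2, SD 10, two-sided 0.05, 75 randomised and about 60 completing per arm (SAP 5.1.1); four arms, 1:1:1:1 (SAP 3.3).

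**The plan's own figure.** With n = 60 per arm, SE = 10 × √(2/60) = 1.826 and the noncentrality is 5.2/1.826 = 2.85. The noncentral t with 118 df gives power of 80.6%, so the stated power of at least 80% reproduces.

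**How much could be missing.** Implied non-completion is 1 − 60/75 = 20%. This is not the share of missing Week 12 PANSS. Early Termination scores from Day 78 count as Week 12, and patients with no post-baseline PANSS are outside the Efficacy Population; visits missed by completers add to the share. I therefore show d = 10%, 20% and 30%, assumed equal across arms.

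**Tipping shift.** If active-arm patients with missing scores average δ points worse than MAR predicts, the estimate falls by d × δ. Significance is lost at

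δ = (estimate − t × SE) / d

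I bracket SE between completers only, SD × √(2/(75(1−d))), and no information lost, SD × √(2/75), with t on 4(n−1) df.

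Worked case, d = 20%, SD 10, estimate 5.2:
- completers only: 1.970 × 1.826 = 3.60; (5.2 − 3.60)/0.2 = 8.0
- no information lost: 1.968 × 1.633 = 3.21; (5.2 − 3.21)/0.2 = 9.9

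| SD | Missing | Estimate 5.2 | Estimate 4.0 |
|---|---|---|---|
| 10 | 10% | 18.1 to 19.9 | 6.1 to 7.9 |
| 10 | 20% | 8.0 to 9.9 | 2.0 to 3.9 |
| 10 | 30% | 4.5 to 6.6 | 0.5 to 2.6 |
| 8.66 | 20% | 10.4 to 12.1 | 4.4 to 6.1 |

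SD 8.66 is an assumed residual SD after baseline adjustment: 10 × √(1 − 0.5²), for a baseline-change correlation of 0.5.

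**A reference point: complete loss of benefit.** If active-arm patients with missing scores end like placebo, the estimate becomes estimate × (1 − d). At d = 20%:
- 5.2 × 0.8 = 4.16. The smallest significant difference is 3.21 to 3.60 at SD 10, so significance holds. Tipping would need these patients to be 8.0 − 5.2 = 2.8 to 9.9 − 5.2 = 4.7 points worse than placebo.
- 4.0 × 0.8 = 3.20. This is just short of significance at SD 10 and significant at SD 8.66, where 2.78 to 3.11 is needed.

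At d = 10%, 4.0 × 0.9 = 3.60, above the 3.21 to 3.39 needed at SD 10.

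**Simulation of the proposed analysis.** Settings: four arms of 75, PANSS at Weeks 2, 4, 8, 10 and 12, baseline covariate, monotone dropout after Week 2, d = 20%, 50 imputations, Rubin's rules, 120 replicates, assumed adjacent-visit correlation 0.6 or 0.9. Median tipping shifts:

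| Baseline-change correlation | Estimate 5.2 | Estimate 4.0 |
|---|---|---|
| 0 | 7.6 to 8.5 | 2.1 to 3.1 |
| 0.5 | 9.6 to 10.3 | 4.3 to 5.1 |

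At 5.2 these run a little below the closed form, because shifting imputed values adds variance. The 10% and 30% rows were not simulated.

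**The case against.** The plan states its assumption, names a sensitivity analysis, and is consistent between protocol and SAP. This is a Phase 2 study of three doses that openly forgoes multiplicity adjustment, so an exact tipping value for nominal p-values may seem a refinement. The arithmetic also points largely to robustness: at the planned effect and 20% missing, patients with missing scores would have to do worse than placebo. Fragility appears only with a smaller estimate or more missing data. All of that stands. It bears on how serious the gap is, not on whether it exists: each dose is still tested at 0.05, and whether the estimate will be 5.2 or 4.0 is unknown.

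Three further points have some force:

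- **Missed visits may be few.** Protocol 7.1 permits remote efficacy assessment, and an unscheduled PANSS from Day 78 can fill Week 12. The protocol allows for missed assessments without predicting their number.
- **The COVID-related population removes some affected patients.** Its definition excludes those whose clinic access was restricted, and pandemic-driven misses are among the more plausible cases for MAR. The reduced set is still analysed under MAR.
- **Early Termination scores support MAR.** They give the model data near withdrawal, but perhaps not always. Table 2 places Days 36 to 49 in Week 6, where no PANSS is scheduled, and its windows begin at Day 8. The SAP does not say how such PANSS values enter the model.

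The closed-form values also run somewhat high against the simulation, as shown above. That changes the illustration slightly and leaves the point intact.

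**Conclusion.** The concern holds. Neither document contains a delta-adjusted, tipping-point, reference-based or other graded departure from MAR, so no planned output can say what would overturn a Week 12 comparison.

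The size depends on results not yet seen. With 20% missing, an estimate at the planned effect looks sturdy, while a significant estimate of 4.0 could tip at a shift of about 2 points or withstand one of about 6, depending on the residual SD and the information retained. These values assume equal missingness across arms, a shift in the active arm only, and the SDs shown; they are not predictions.

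The primary analysis is not invalid and the sample size is unaffected. This is an inexpensive improvement that should be made before unblinding.

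**What to change.** In SAP 5.1.4, before unblinding, pre-specify a delta-adjusted tipping-point analysis of Week 12 PANSS total in the Efficacy Population:

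- Multiply impute missing values under MAR, using the terms of the primary MMRM.
- Worsen the imputed active-arm values in fixed steps, for example 2 points.
- Combine by Rubin's rules, and report for each dose against placebo the step at which significance is lost.
- State whether Week 12 values missed by completers are shifted too or left at MAR.

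Control-based multiple imputation may be added but does not suffice alone, because it is also a single fixed assumption. LOCF can remain as a descriptive table.

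The cost is SAP wording and some programming, with no new data and no change to the primary analysis. The sponsor should accept that these supportive results will usually look less favourable than the MMRM.

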#### **5.1.5 Study Day and Visit Window Definitions**

The baseline assessment for all efficacy endpoints is defined as last assessment prior to the first dose of Study Medication on Day 1. Data obtained during unscheduled and at the Week 12/Early Termination early visits will be allocated to the scheduled time point corresponding to the visit window in which they fall in as specified in Table 2. For patients completing the study, data will be analyzed based on the nominal visits and nominal time points. If the data from the nominal visit or time point are missing or the patient did not complete the study, data from

unscheduled visits or the Week 12/Early Termination visit within the time interval for the same nominal visit or time point will be used. If multiple visits among unscheduled or Early Termination assessments fall in the same visit window or time point, the non-missing assessment closest to target time point will be selected for analysis. If multiple values are the same number of days away from the target study day, then the latter value will be used. In the unlikely event an unscheduled or Early Termination visit, associated with a particular visit window, falls either prior to the actual previous nominal visit date or after the subsequent nominal visit date, it will not be used. This is done simply to ensure the data assigned to particular analysis time points will not be out of sequence.

The first date on which patient received the Study Medication will be used as the Study Day 1. Study days for other visits will be calculated as follows:

- Before Study Day 1 visit: Study Day = date of assessment – date of Study Day 1
- On or after Study Day 1 visit: Study Day = date of assessment – date of Study Day 1 + 1

Last study date is the last visit date of any scheduled, unscheduled, or Early Termination visits. Last Study Day is calculated as:

- Last Study Day = last study date – date of Study Day 1 + 1

The target study days of Study Center Visits are summarized below.

**Table 2 – Guidelines for Assigning Unscheduled and Early Termination Visits for Efficacy Assessments**

Week/Visit	Time Interval (Day)	Target Time Point (Day)
-5/Screening	Use nominal	-35*
-3/Qualification	Use nominal	-24 to -21*
1 (Baseline/Day 1)	Last assessment prior to dosing	1
2	8 to 21	14
4	22 to 35	28
6	36 to 49	42

8	50 to 63	56
10	64 to 77	70
12	78 to 1 day prior to Safety Follow-up	84
13/Safety Follow-up	Use nominal	91

\*5-week Screening/Qualification Period may be extended up to 2 weeks if repeat laboratory test results for confirmation of eligibility are pending.

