- Standard 12-lead ECG (Weeks 6 and 12 only; if Week 6 visit is a remote visit, ECG assessment may be performed at Week 8 or 10)
- Urine pregnancy tests for women of childbearing potential
- Alcohol breath test
 - o *Patient may be discontinued if they test positive at any two visits during the treatment period*
- Serum chemistry, hematology, and coagulation parameter evaluations (Weeks 6 and 12 only)
- Serum renal parameters and urinalysis
- Blood sample for assessment of CTP-692 levels (pre-dose if dose of Study Medication is administered in the clinic at Weeks 2, 4, 6, 8, and 10)
 - o *If possible, time of last dose taken should also be recorded*
- Dispensation of Study Medication to take home
 - *A 2-week supply of the Study Medication will be provided at each visit except Week 12*
 - *When study assessments are not conducted in the clinic due to the COVID-19 pandemic, the Study Medication may be sent directly to the patient*
- PANSS (Weeks 2, 4, 8, 10, and 12)
- CGI-S (Weeks 2, 4, 6, 8, 10, and 12)
- C-SSRS (Since Last Visit version)
- PSP (Weeks 6 and Week 12 only)
- SQLS (Week 12 only)
- SAS, AIMS and BARS (Weeks 6 and Week 12 only)
- Blood sample for assessment of CTP-692 levels (post-dose; Week 12 only)
 - *Blood sample should be taken at the end of the visit*
 - *Time of CTP-692 dose and blood draw should be recorded*
- Administration of dose of Study Medication in the clinic with food *at the Week 12 visit*
 - Post Dose blood sample for assessment of CTP-692 levels (Week 12 only)
 - o *Blood sample should be taken at the end of the visit*
 - o *Time of CTP-692 dose and blood draw should be recorded*

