9.3. Patient Withdrawal Criteria

Patients may withdraw from participation in the study at any time. The Investigator may withdraw a patient at any time if they believe the safety of the patient or the integrity of the data are at risk. In addition, patients should be withdrawn if they:

- Experience a serious or intolerable AE
- Develop a clinically significant laboratory or ECG abnormality
- Develop proteinuria of 1-2+ or UACR > 30 mg/g as confirmed by a repeat lab test
- Develop eGFR levels < 60 mL/minute/1.73 m² as confirmed by a repeat lab test
- Develop *symptomatic* ALT or AST elevation ≥ 2 x the ULN on two repeat lab tests or develop *asymptomatic* ALT or AST elevation ≥ 3 x the ULN as confirmed by a repeat lab test
- Develop total bilirubin ≥ 2 x the ULN as confirmed by a repeat lab test
- Exhibit suicidal behavior as determined by an affirmative answer on items 4 or 5 on the C-SSRS
- Do not follow guidelines specified in the protocol (i.e., is noncompliant with protocol procedures or Study Medication administration) or specific instructions by the study staff
- Any medically appropriate reason or significant protocol violation, in the opinion of the Investigator
- Are lost to follow up

In case of two consecutive missed safety assessments due to the COVID-19 pandemic, continued patient participation in the study must be discussed by the Investigator and the Medical Monitor.

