9.3.1. Patient Withdrawal Procedures

A patient who prematurely discontinues Study Medication/study participation should have all Week 12 assessments performed as an Early Termination Visit, and if possible, return for the Safety Follow-up Visit. In light of the COVID-19 pandemic, study personnel should strive to perform assessments per [Table 6](#) with the understanding that not all assessments may be able to be performed. All missed assessments will be documented in the eCRF with notation that the missed assessment was due to the COVID-19 pandemic. The Safety Follow-Up Visit may be waived by the Sponsor in instances where patients have discontinued dosing prior to the Early Termination Visit on a case-by-case basis.

If a patient terminates early from the study, the Investigator will record the reason(s) for early termination on the relevant electronic case report form (eCRF). The specific reason for the withdrawal should be carefully documented on the eCRF.

Adverse events resulting in patient early termination will be followed to the satisfactory resolution and determination of outcome, as ascertained by the Investigator (and/or Sponsor, or its designee); (See Section 12). The data will be recorded on the appropriate eCRF.

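### SAP Table 2 sends an Early Termination PANSS from Days 36 to 49 to Week 6, where PANSS is not analysed, so it gets no weight in the Week 12 estimate (small effect, cheap to correct)

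*SAP*

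**What the plan says.** - **Early Termination assessments.** Protocol 9.3.1: "A patient who prematurely discontinues Study Medication/study participation should have all Week 12 assessments performed as an Early Termination Visit". PANSS is one of the Week 12 assessments.
- **Placement of those data.** Under SAP 5.1.5, data from unscheduled and ET visits "will be allocated to the scheduled time point corresponding to the visit window in which they fall in as specified in Table 2". Table 2, "Guidelines for Assigning Unscheduled and Early Termination Visits for Efficacy Assessments", is a single table for all efficacy instruments. Week 4 is Days 22 to 35, Week 6 is Days 36 to 49 (target Day 42), and Week 8 is Days 50 to 63 (target Day 56).
- **When PANSS and PSP are rated.** Protocol 8.2.2 lists "PANSS (Weeks 2, 4, 8, 10, and 12" and "PSP (Weeks 6 and Week 12 only". CGI-S is rated at every clinic visit, Week 6 included.
- **Where PANSS is analysed.** SAP 4.4.3 and 5.4.3 list Weeks 2, 4, 8 and 10 besides the primary Week 12. SAP 5.1.2.4 describes the Per-Protocol analyses as "restricted to the change in PANSS Total Score at weeks 2, 4, 8, 10, and 12".
- **The model.** SAP 5.4.1 specifies an MMRM with treatment-by-visit and baseline-by-visit terms and an unstructured covariance. SAP 5.1.4 imputes nothing in the primary analysis, relies on missing at random (MAR), and adds LOCF as a sensitivity analysis.

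Neither document gives PANSS its own windows or says what happens to a PANSS that Table 2 places at Week 6.

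**The concern.** The Week 6 row suits CGI-S and PSP, which are rated then. For PANSS it leads nowhere. A patient who stops on Day 33 or Day 52 has the ET PANSS placed at a PANSS visit; a patient who stops on Day 42 does not, and the documents give no reason for the difference.

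This matters because the primary analysis rests on MAR, under which withdrawal may depend on scores that are in the model. The ET PANSS is the score closest to the decision to stop. If patients leave because they worsened after Week 4, that worsening was measured but is not modelled, and the Week 12 comparison could move. The direction would depend on the arm in which it happens. The COVID-related and Per-Protocol PANSS analyses use the same windows.

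**Working it through.** **1. The plan's own figure.** Inputs from SAP 5.1.1: difference 5.2, SD 10, 60 per arm, two-sided 0.05.

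- Standard error = 10 × √(2/60) = 1.83
- Power ≈ Φ(5.2/1.826 − 1.960) = Φ(0.888) = 81.3%; the noncentral t gives 80.6%

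The stated power of at least 80% is reproduced. The plan randomises 75 per arm "to achieve a sample size of approximately 60 patients per arm who complete the study", so it expects 75 − 60 = 15 non-completers per arm.

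**2. Table 2 set against the rating schedule.**

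| ET day | Table 2 visit | PANSS analysed? | PSP rated? |
|---|---|---|---|
| 8–21 | Week 2 | yes | no |
| 22–35 | Week 4 | yes | no |
| 36–49 | Week 6 | **no** | yes |
| 50–63 | Week 8 | yes | no |
| 64–77 | Week 10 | yes | no |
| 78 onward | Week 12 | yes | yes |

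**3. Would a Week 6 level in the model rescue the score?** No. Unscheduled ratings apart, nobody has both a Week 6 and a later PANSS. Given Weeks 2 and 4, the Week 6 scores then have their own free parameters (arm means, baseline slope, regression on the earlier visits, residual variance). That part of the likelihood separates from the part that determines Week 12. Numerical checks on simulated data:

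- Maximum likelihood, 4 × 75 patients, 3 ET scores per arm per window, 5 data sets: the Week 12 differences with Week 6 dropped and with Week 6 kept agree to 4.5 × 10⁻¹⁰.
- REML, one two-arm data set, 3 such patients per arm: −5.2101 dropped, −5.2101 kept, −5.1764 with the score placed at Week 8.

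Only placement at a visit that continuing patients also have lets the score count. These checks cover point estimates. Kenward-Roger standard errors and degrees of freedom were not compared.

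**4. How many scores.** Stop timing is not in the documents, so it is assumed, as is an ET rating for every non-completer.

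- Uniform over Days 2 to 84 (83 days): 15 × 14/83 = 2.53 per arm, about 10 in the trial
- Weibull timing with 20% stopped by Day 84, shapes 0.6 to 2.0: 1.9 to 2.7 per arm

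Under each timing assumption these are upper limits.

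**5. How far the Week 12 difference moves.** By hand: suppose 2.53 of 75 patients in one arm have ET scores 5 to 10 points worse than predicted, with correlation 0.8 to Week 12 (both assumed).

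- 2.53/75 × 5 × 0.8 = 0.13
- 2.53/75 × 10 × 0.8 = 0.27

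By simulation: two arms of 75, 15 stops per arm, true difference growing linearly to 5.2, SD at Week 2 of 6, 8 or 10 rising to 10, correlation 0.7 to 0.9 per two weeks, 2,500 trials per case, Monte Carlo error 0.010 to 0.015. In the adverse case, the patients in one arm who worsened most between Weeks 4 and 6 leave in the window.

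| Such patients | Shift, ET score unused | Shift, ET score at Week 8 |
|---|---|---|
| 2 | 0.12 to 0.20 | up to 0.08 |
| 3 | 0.19 to 0.30 | up to 0.10 |

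Against the standard error: 0.12/1.83 = 7% and 0.30/1.83 = 16%. With stopping unrelated to symptoms, the shift is at most 0.04 under either handling.

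**6. PSP.** The same mapping leaves ET PSP scores on Days 8 to 35 and Days 50 to 77 at visits where PSP is not rated. Under the same uniform assumption that is 15 × 28/83 = 5.1 per arm in each band. No PSP shift was computed.

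**The case against.** The strongest reply is that this is immaterial. The 0.1 to 0.3 points need the worst-worsening patients to leave in one fortnight and in one arm only. That stands, and it sets the severity.

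Not every withdrawal produces an ET rating. The list in Protocol 9.3 that opens "In addition, patients should be withdrawn if they" includes loss to follow-up, and 9.3.1 accepts that assessments may be missed because of COVID-19. That also stands, so the counts are ceilings. Nor is the patient lost: the Week 2 and Week 4 scores stay in the MMRM.

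Placing the score at Week 8 has a cost. A Day 36 rating is 56 − 36 = 20 days before the Week 8 target and only 8 days after the Week 4 target. This is fair, but the patient normally already has a Week 4 score, and one of the two would be displaced. No Week 8 score is displaced, because the patient has left.

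LOCF, on its ordinary meaning, would carry the ET PANSS forward, so the sensitivity analysis probably uses it. I accept this; a sentence saying so would only be a clarification.

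A reader might go further and infer inflated Type I error: a Week 6 level fails to converge and the SAP falls back to Toeplitz. The documents do not support that. No PANSS visit list includes Week 6, and nothing shows that the fit would fail.

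**Conclusion.** The gap is real and follows from applying Table 2 as written. An ET PANSS on Days 36 to 49 is assigned to a visit without a PANSS analysis and, unscheduled ratings apart, has no weight in the primary Week 12 estimate. The separation argument is exact where Weeks 2 and 4 were both rated. That Week 6 is not a model visit is inferred from the endpoint lists, because SAP 5.4.1 does not name the levels, but the Week 12 point estimate is the same either way.

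The size is small: at most about 2.5 scores per arm with uniform timing, and a shift of 7% to 16% of one standard error in an assumed one-arm adverse case. The shift is about zero if stopping is unrelated to symptoms. A reader might infer that the primary result is biased in a known direction. The documents give neither the timing nor the reasons for stopping by arm, so no direction can be stated. This is a cheap improvement of low severity.

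**What to change.** Before database lock:

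1. In SAP Table 2, add: *For PANSS, an Early Termination score on Days 36 to 49 is assigned to Week 8, the next visit at which PANSS is scheduled.*
2. In SAP 5.4.1, state that the PANSS model visits are Weeks 2, 4, 8, 10 and 12.

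Optionally, say in SAP 5.1.4 that LOCF carries forward the last PANSS, including one taken at Early Termination.

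The cost is two SAP sentences, with no protocol amendment and no extra patients, visits or ratings. The downside is that a score 7 to 20 days ahead of target enters Week 8, which slightly affects that exploratory estimate. In the adverse case a shift of up to 0.10 points remains.

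I do not propose PSP windows here. Sending Days 8 to 35 to Week 6 would label a Day 8 score as one due 34 days later, and Days 50 to 77 would still need a rule. The sponsor should decide that trade-off and write the PSP rule down separately.
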